3.5 Tether

The Capsule Tether is an optional component which allows the visualization of the esophagus. The component is comprised of soft tubing which on one end is attached to a capsule cradle (to hold the capsule in place) and on the other end attaches to a 20ml standard syringe injection of water by the syringe detaches the capsule from the tether. (Figure 8).

[figure not shown]

Figure 8: Capsule Tether

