4 STUDY OBJECTIVES

4.1 Study Objectives

Primary:

1. To demonstrate the effectiveness of the MCC and MCC-T when compared to EGD in identifying esophageal, gastric and duodenal abnormalities in patients presenting with upper abdominal symptoms.
2. To evaluate rates of adverse events and overall safety of MCC-T as compared to EGD.

Secondary:

1. To compare rates of complete examination of the foregut by MCC, MCC-T and EGD in patients presenting with upper abdominal complaints using sets of predetermined still images
2. To assess patient satisfaction for patients undergoing MCC, MCC-T and EGD.

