4.2 Study Endpoints

Primary

Effectiveness:

For both MCC, MCC-T and EGD, rates of diagnosis of clinically relevant pathology in patients with upper abdominal pain will be assessed. Detection of D2 findings will be considered positive. Sensitivity, specificity, positive predictive value, and negative predictive values will be calculated for both MCC and EGD. In this study the “gold standard” will be the expert group’s decision regarding the presence of an abnormal finding. McNemar’s test will be used to assess for statistically significant differences between the two modalities. Sub-analyses will be performed to compare accuracies of the two modalities based on anatomic region (i.e. esophagus, stomach, duodenum) and across various lesions (i.e. ulcers, gastropathy, esophagitis, etc.).

Safety: Rate of device or procedure related adverse events during the procedures or in the follow-up period (24 hrs. post procedure).

Secondary

Examination completion: Compare rates of complete examination of the foregut by MCC or MCC-T and EGD in patients presenting with upper abdominal complaints using sets of predetermined still images

Patient Satisfaction: Assess patient satisfaction for patients undergoing MCC or MCC-T and EGD.

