6.5 Visit 2 – MCC, MCC-T and EGD Procedure

Upon being checked in, the subject will be brought to the study area with the NaviCam System. A study staff member (NP/Attending/Fellow) trained in the MCC-T procedure will review the study procedure with the patient and confirm that the patient has been NPO for at least 8 hours. The patient will drink about 250ml of water prior to ingesting the capsule containing 1-2 drops of simethicone (infant formulation).

Examination of Esophagus:

The sensor array jacket will be attached to the patient. After the capsule is activated the patient will swallow the capsule (attached to a tether) in the sitting position. It will then be slowly lowered down the esophagus for a complete exam. Alternatively, the patient will be placed in the prone position with a 10° elevation of the head and ingest the capsule without the tether using sips of water. The study staff member will then record the video of the examination of the esophagus by moving the capsule down the esophagus using the magnetic field.

Images to be obtained:

1. Upper esophagus

2. Middle esophagus
3. Lower esophagus
4. Z line.
5. Any pathological lesions

Examination of Stomach:

Once the examination of the esophagus is complete and the capsule is in the stomach, the tether, if used, will be used to view the stomach as the patient drinks about 500 to 1000 cc of water with 4 drop of simethicone to ensure adequate gastric distention. The tether is then detached from the capsule by injecting air through the tether causing separation of the two components. The tether is withdrawn. Then instructed to lay down per physician instructions. The study staff member will begin controlling the device using the magnetic system. The patient will move their position in a predetermined patent to enhance complete visualization of the stomach as was done in the esophagus, a video will be recorded of the full examination. Photo documentation in accordance with a gastric mapping protocol will also be done. This includes images of the following:

- Distal Antrum
- Centered view of the pylorus
- Proximal Antrum
- Two pictures along the length of the incisura
- Distal body
- Mid/proximal body (lesser curvature)
- Mid/Proximal body (greater curvature)
- Gastric fundus
- Gastric cardia
- Any gastric pathology (e.g. gastric varices, gastric ulcers, gastropathy, polyps, etc.)

Examination of duodenum:

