10.5 Efficacy Analysis

1) Clinical success – Diagnostic yield

For both MCC-T and EGD, we will be assessing rates of diagnosis of clinically relevant pathology in patients with upper abdominal pain. Detection of D2 findings will be considered positive. Sensitivity, specificity, positive predictive value, and negative predictive values will be calculated for both MCC-T and EGD. In this study the “gold standard” will be the expert group’s decision regarding the presence of a relevant finding. McNemar’s test will be used to assess for statistically significant differences between the two modalities. Sub-analyses will be performed to compare accuracies of the two modalities based on anatomic region (i.e. esophagus, stomach, duodenum) and across various lesions (i.e. ulcers, gastropathy, esophagitis, etc.).

2) Secondary Outcomes

Technical success:

- i. We will assess the ability of the -MCC-T and the EGD to photo document the esophagus, stomach, and duodenum as described in this protocol.
- ii. We will assess the ability of the MCC-T to be released upon command in the stomach once esophageal examination is complete.

Learning curves:

When training staff to use the device, we will assess how many capsules it takes to obtain “competency.” This will be defined as being able to obtain the appropriate photo documentation as described above at a 90% success level.

Patient satisfaction

Patient responses will be analyzed on a Likert scale to determine which procedure did the patients prefer.

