10.6 Sample Size

Since there is no predicate data in the United States we have elected to do a pilot study involving 70 patients and up to 30 volunteers who will help the investigators optimize the technique with the MCC and MCC-T. We will allocate patients to MCC or MCC-T randomly using a randomization protocol generated by Redcap

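### The examination-completion endpoint leaves *complete* undefined and pools the whole foregut, which can dilute any effect of the tether on esophageal imaging; completion should also be reported by region

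*Combined protocol and SAP*

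**What the plan says.** Section 4.1 sets the secondary objective: "To compare rates of complete examination of the foregut by MCC, MCC-T and EGD". Section 4.2 restates it as an endpoint, to "Compare rates of complete examination of the foregut by MCC or MCC-T and EGD in patients presenting with upper abdominal complaints", and bases the judgment on image sets: "using sets of predetermined still images". Neither section says how many images make an examination complete.

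The images are listed in section 6.5. Under "Images to be obtained" there are four esophageal landmarks (upper, middle, lower, Z line). For the stomach, "Photo documentation in accordance with a gastric mapping protocol will also be done", with nine landmark entries that make ten pictures because the incisura counts twice. The duodenal bulb is also photographed. Pictures of pathology are extra. EGD is to produce the same set.

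Section 3.5 gives the purpose of the tether: "The Capsule Tether is an optional component which allows the visualization of the esophagus". Section 10.6 randomizes between the two capsule versions: "We will allocate patients to MCC or MCC-T randomly using a randomization protocol generated by Redcap".

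Section 10.5 turns the endpoint into technical success, meaning the ability to photo-document the three organs. It names only MCC-T and EGD and gives no scoring rule and no test. The sub-analyses by anatomic region in 4.2 and 10.5 concern diagnostic accuracy, not image completion.

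**The concern.** A rate of complete examinations is one yes or no per examination, taken over the whole foregut. If *complete* means every listed image, an examination that misses one image scores the same as one that misses ten. A difference confined to the esophagus must then show through whatever happens in the stomach and duodenum.

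This matters because patients are randomized between MCC and MCC-T. That is the study's only randomized evidence on what the tether adds, and section 3.5 places the expected benefit in the esophagus. If the only completion figure is a whole-foregut rate, a real gain in esophageal imaging could be reported as little or no difference. An undefined *complete* also leaves the scoring rule open to choice after the images have been seen.

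**Working it through.** The plan has no figure to reproduce. Section 10.6 chooses the sample size as a pilot, with no significance level, power or expected completion rate.

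**Inputs from the documents.** Images per examination (6.5): 4 + 10 + 1 = 15, of which 11 are not esophageal. Patients (10.6): 70.

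**Assumptions.** Allocation 1:1, so 70 / 2 = 35 per group; two-sided 5% test; esophageal image success 85% (MCC) v 95% (MCC-T); the same success in both groups on each of the other 11 images, set at 90%, 97% or 99%; within-region correlation of image failures 0 to 0.3; *complete* means all 15 images.

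**Step 1: dilution when failures are independent.** The esophagus is complete in 0.85^4 = 52.2% v 0.95^4 = 81.5%, a difference of 29.3 points. The foregut rate multiplies both by q, the chance that the other 11 images are all obtained: 0.90^11 = 0.314, 0.97^11 = 0.715, 0.99^11 = 0.895. The products are in the second column below.

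**Step 2: power.** Trials were simulated with beta-binomial image success, comparing a two-proportion test on the foregut rate with a rank-sum test on the esophageal count out of 4. Ranges run over the correlations.

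| Success on each other image | Foregut complete, MCC v MCC-T (independent) | Power, foregut rate | Power, esophageal count |
|---|---|---|---|
| 90% | 16.4% v 25.6% | 15–18% | 61–78% |
| 97% | 37.3% v 58.3% | 37–40% | 60–79% |
| 99% | 46.7% v 72.9% | 50–63% | 60–78% |

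The last column does not depend on the first; its small differences are simulation error. A repeat with 4,000 simulated trials per scenario agreed within about 2 points.

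**Step 3: cross-check by formula.** For rates p1 and p2 with mean m and n per group, power = Φ{(|p2 − p1|√n − 1.96√[2m(1 − m)]) / √[p1(1 − p1) + p2(1 − p2)]}. Take esophagus-complete rates of 60% v 90% and n = 35.

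- Esophagus alone: (0.30 × 5.916 − 1.96 × 0.612) / 0.574 = 1.00, so power is 84%.
- Foregut with q = 0.6, rates 36% v 54%: (0.18 × 5.916 − 1.96 × 0.704) / 0.692 = −0.45, so power is 33%.
- At q = 0.95, 0.8 and 0.4, power is 76%, 54% and 19%.

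Across assumed esophagus-complete rates of 50% v 80%, 60% v 90% and 50% v 90%, half the power is gone only when q falls below about 0.56–0.70 with 35 per group, or 0.46–0.63 with 50 per group. For 80% power at 60% v 90%, the number per group is 32 for the esophagus alone, 65 at q = 0.8 and 119 at q = 0.6.

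**Step 4: where the loss comes from.** With 85% v 95% and correlations 0, 0.1 and 0.3, a yes/no for the esophagus alone had power 77%, 71% and 61%, against 79%, 73% and 62% for the count. Pooling the regions causes nearly all the loss; using a yes/no causes little.

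**Step 5: capsule versus EGD.** For 70 paired examinations over all 15 images, replacing the complete rate with a count raises power by up to 43 points when failures are independent (85% v 90%: 49% to 92%). It gains little, or loses up to about 10 points, when failures are strongly correlated.

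**The case against.** The strongest reply is that no tether test exists to lose power. Section 4.2 sets either capsule against EGD, the endpoint is secondary, and this is a pilot without a hypothesis. That stands as a limit on severity. It does not remove the point: 4.1 lists MCC, MCC-T and EGD separately, and the plan randomizes between the capsules.

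Four stronger readings are tempting, and the documents do not support them.

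- A reader might infer that the plan requires all 15 images. It never says so. Section 4.2 speaks of image sets in the plural, 6.5 uses completeness organ by organ, and 10.5 lists the organs without a composite. All-or-nothing is the natural reading, not a stated rule.
- A reader might infer that most of the power is lost. That holds only when gastric and duodenal success is low. With 70% v 90% esophageal success and 97% elsewhere, the foregut rate has 70–79% power against 89–98% for the count; at 99% elsewhere it has 82–90%.
- A reader might take the competency level in 10.5 as 90% per image and infer a floor of 0.9^15 = 21% complete examinations. The text reads: "This will be defined as being able to obtain the appropriate photo documentation as described above at a 90% success level". It could equally mean the full set in 90% of examinations, in which case there is no floor.
- A reader might infer that a count should replace the complete rate throughout. Steps 4 and 5 do not support this.

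One further objection stands in part. Section 6.5 has the tether, if used, in place while the stomach is first viewed, so equal gastric success in the two groups is an assumption. Gastric results should be reported beside the esophageal ones.

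**Conclusion.** The point holds as a cheap improvement to a secondary endpoint. The firm defects are that *complete* has no definition and that image completion has no planned comparison by region covering both capsule versions. The dilution is certain in direction if every image is required and the tether acts only on the esophagus. In the table, the cost ranges from about 10–15 points of power at 99% success elsewhere to more than 40 points at 90%.

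These sizes rest on assumed success rates, correlations and allocation. The number per group is itself uncertain. The synopsis gives 100 patients plus 10 volunteers, section 5.2 up to 100 including up to 30 volunteers, and 10.6 has 70 plus up to 30. With 50 per group, 85% v 95% and 90% elsewhere, power is 21–25% against 59–92% for correlations 0 to 0.6, so the ordering does not change.

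A separate obstacle bears directly on the tether comparison. Section 10.2 defines the population for all safety and efficacy analyses by ingestion of the tethered capsule. Read literally, that leaves no MCC group to compare.

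**What to change.** In sections 4.2 and 10.5:

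- State what makes an examination complete, by listing the required images and saying whether all are needed.
- Keep the whole-foregut complete rate as the comparison of capsule with EGD.
- Add images obtained by region (esophagus out of 4, stomach out of 10, duodenum out of 1) for MCC, MCC-T and EGD separately.
- Name one esophageal measure, compared between the randomized MCC and MCC-T groups, as the main tether comparison. Either the count out of 4 (rank-sum test) or the esophagus-complete rate will do. Report the gastric images beside it.

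In section 10.2, amend the analysis population so that patients given the untethered MCC are included.

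The cost is wording and a little more analysis. The images are already required in every examination, so no extra procedure or patient is needed. The downside is that several regional results will be reported, which is why one must be named in advance as the main one.

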5 INVESTIGATION DESIGN

5.1 Study Design

This study is a prospective, single center, tandem study designed to evaluate the safety and effectiveness of the MCC, MCC-T compared with EGD.

5.2 Patient Population

Approximately 400 patients a month are seen in the UMass Gastroenterology outpatient clinic or are referred for EGD with complaints of upper abdominal pain requiring an upper endoscopy. These patients will be screened for possible inclusion in the study the day prior to their visit to the clinic.

A total of up to 100 patients will be enrolled in the study, including up to 30 healthy volunteer participants for training.

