Exclusion Criteria	
 1. Patient with dysphagia. 2. Patient with previous intestinal surgery. 3. Patient with Crohn's disease or other potential obstructive conditions, unless there is a recent CTE, MRE or patency capsule performed to exclude an obstructive lesion that may retain the capsule. 4. Female patient who is pregnant. 5. Patient with implanted medical device that would be potentially affected by magnets or radiofrequency emissions (e.g., pacemakers, implanted cardiac defibrillators). 6. COVID-19+ or with symptoms consistent with the infection. Fever, new cough, myalgias, and chills
Study Population and Sample Size	Since there is no predicate data in the USA, we plan a pilot study with 100 patients and 10 volunteers to help optimize the use of the MCC and MCC-T

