5.4 Inclusion Criteria

The inclusion criteria for this study are:

1. Patient is 18-75 years
2. Patient is able to provide informed consent
3. Patient has appropriate indications for EGD including symptoms of, but not limited to upper abdominal pain, acid reflux, heartburn, iron deficiency anemia, weight loss, bloating, belching, nausea, vomiting and atypical chest pain.
4. Patients are COVID-19 negative by PCR testing 1-3 days prior to MCC/MCC-T and EGD or fully vaccinated against SARS-CoV-2 (at least two weeks after final dose of authorized or approved vaccine) and completion of a symptom screening questionnaire before participating in the study.

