5.8 Screening Failure

Patients who have not fulfilled all the inclusion criteria or have fulfilled one of the exclusion criteria will not be included in this study. Screening failures will be replaced by suitable candidates.

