6.7 Identification of relevant lesions

On a weekly basis, 2 study attendings will independently review the results of the EGDs/MCCs that were performed during the week and complete a report sheet. A per-patient analysis of any abnormal lesion/s will be performed. During this analysis, the physicians will be asked if either the MCC or MCC-T or the EGD identified a lesion that would be of high likelihood to explain the patient's symptoms. If a responsible lesion is identified, then the physicians will review both the MCC and EGD to see if the lesion(s) were identified on both exams. Findings will be graded on a three-tier scale as follows:

- **D0:** finding is unlikely to be related to patient's presenting complaint
- **D1:** finding is of a medium likelihood to be related to the patient's presenting complaint
- **D2:** finding is of a high likelihood to be related to the patient's presenting complaint.

In addition, reviewing group will be responsible to perform a per-lesion analysis to assess whether all findings identified on the MCC and/or EGD were seen on the other exam (regardless of whether the finding is relevant to the patient's complaint). The statistician will then compare the results and obtain a Kappa statistic of the three sets of observations. And perform a statistical analysis as outlined under the analysis section.

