10.2 Study Populations

The safety population will include all subjects who swallowed the NaviCam Capsule with tether and underwent upper endoscopy. All safety and efficacy analyses will be performed on the safety population.

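### Healthy volunteers are counted among the 100 patients although the only inclusion list requires an EGD indication, and the single analysis set neither excludes them from efficacy nor secures them for safety

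*Combined protocol and SAP*

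**What the plan says.** Section 5.2 sets enrolment: "A total of up to 100 patients will be enrolled in the study, including up to 30 healthy volunteer participants for training". Section 10.6 describes "a pilot study involving 70 patients and up to 30 volunteers", the volunteers being there to help the investigators refine technique with both versions of the capsule. The synopsis gives other numbers: "we plan a pilot study with 100 patients and 10 volunteers".

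One set of inclusion criteria appears, in 5.4 and in near-identical form in the synopsis. Criterion 3 begins "Patient has appropriate indications for EGD including symptoms of, but not limited to upper abdominal pain" and goes on to list further symptoms. Section 5.8 adds: "Patients who have not fulfilled all the inclusion criteria or have fulfilled one of the exclusion criteria will not be included in this study". The text gives volunteers no entry criteria and no visit schedule of their own. The table in 6.2 and the procedures in 6.4 and 6.5 describe a capsule examination followed by EGD.

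Section 10.2 defines one analysis set: "The safety population will include all subjects who swallowed the NaviCam Capsule with tether and underwent upper endoscopy". It continues: "All safety and efficacy analyses will be performed on the safety population".

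A D2 finding makes a test positive, and 6.7 defines D2 as follows: "finding is of a high likelihood to be related to the patient's presenting complaint". Sections 4.2 and 10.5 describe diagnostic yield in patients who have upper abdominal pain, and 4.2 describes completion in patients with upper abdominal complaints. The reference standard is the expert group's decision on a relevant finding in the synopsis and 10.5, and on an abnormal finding in 4.2. Section 10.1 names EGD instead.

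**The concern.** Two things do not fit together.

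The first is eligibility. A healthy volunteer has no indication for EGD and so fails criterion 3. The open-ended symptom list widens what may count as an indication but does not remove the need for one. Read literally, 5.8 then keeps out the people whom 5.2 and 10.6 plan to enrol.

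The second is analysis. Section 10.2 is written without volunteers in mind, and its one rule serves two purposes badly:

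- A volunteer who had the tethered capsule and EGD meets the definition and enters the accuracy analysis, although the endpoint is about symptomatic patients.
- A volunteer who swallowed a capsule and had no EGD fails the definition. That capsule exposure is then lost from the safety analysis, which is a primary endpoint.

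At stake are the denominators of the primary results. Yield, specificity and NPV would partly reflect how many people without symptoms were added. Alternatively, up to 30 of up to 100 capsule exposures would be missing from safety.

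**Working it through.** **Plan's own totals.** Section 10.6: 70 + 30 = 100, which matches 5.2. Synopsis: 100 + 10 = 110, which does not. The documents give no prevalence, sensitivity, specificity or power, so the inputs below are assumptions.

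**Assumed patient data.** 70 patients, 21 with D2 disease, 17 of them found by the capsule: TP = 17, FN = 4, and 49 patients without D2 disease. Add v volunteers, all reference-negative and test-negative (the relevant-finding reference of 10.5).

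Formulas with no false positives: yield = 17/(70 + v); NPV = (49 + v)/(53 + v); accuracy = (66 + v)/(70 + v). With 5 false positives, specificity = (44 + v)/(49 + v).

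| | v = 0 | v = 10 | v = 30 |
|---|---|---|---|
| Yield | 17/70 = 24.3% | 17/80 = 21.3% | 17/100 = 17.0% |
| NPV | 49/53 = 92.5% | 59/63 = 93.7% | 79/83 = 95.2% |
| Accuracy | 66/70 = 94.3% | 76/80 = 95.0% | 96/100 = 96.0% |
| Specificity, 5 false positives | 44/49 = 89.8% | 54/59 = 91.5% | 74/79 = 93.7% |

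**What does not move.** Sensitivity is 17/21 = 81.0% throughout. PPV uses only test-positives, so it stays at 17/17, or 17/22 = 77.3% with 5 false positives. McNemar's test uses only discordant pairs, and a volunteer negative on both tests adds none. For example, with 15 positive on both tests, 3 and 9 discordant and 43 negative on both (n = 70), the exact p is 0.146. With 73 negative on both (n = 100) it is again 0.146.

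**Range.** Take 70 patients, sensitivity 80%, D2 prevalence 10% to 50%, and v = 30. Specificity is (s × N + 30)/(N + 30), where s is the specificity in patients and N, the number without D2 disease, runs from 63 to 35.

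- s = 70%: 74.1/93 = 79.7% to 54.5/65 = 83.8%
- s = 80%: 80.4/93 = 86.5% to 58/65 = 89.2%
- s = 90%: 86.7/93 = 93.2% to 61.5/65 = 94.6%

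Observed D2 prevalence is multiplied by 70/100 = 0.70, for example from 30% to 21%.

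**The other reference standard.** Under 4.2, suppose k of the 30 volunteers have an incidental abnormality. Each is reference-positive but cannot be D2-positive, and so is a false negative. With the patient cells held fixed and no false positives, sensitivity is 17/(21 + k) and NPV is (79 − k)/83. One such volunteer gives 17/22 = 77.3% and 78/83 = 94.0%. Three give 17/24 = 70.8% and 76/83 = 91.6%, below the patient-only NPV of 92.5%. The direction of the NPV effect therefore depends on which reference applies.

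**No EGD in volunteers.** Then v = 0 in the table and the accuracy results are unaffected, but 10.2 removes every volunteer from the safety set.

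**The case against.** The strongest reply is that the plan already treats volunteers as something apart. The eligibility criteria and 5.8 speak of patients, and 10.6 and the synopsis list volunteers separately. Section 10.6 randomises patients only, and 10.5 has a learning-curve outcome. On that view the criteria are patient criteria, the volunteers' own criteria were simply left out, and the endpoint wording keeps volunteers out of the yield analysis.

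Much of this stands. A reader might infer that 10.2 will count the volunteers, or that they are scheduled for a sedated EGD without an indication. The documents do not support either. Section 10.2 requires both tether and EGD, and no section says that volunteers have EGD. The flow diagram in 6.1 and the appended timeline cannot be read in the available text, so they cannot be called silent. A reader might also infer that every volunteer is automatically a true negative, which fails under the abnormal-finding reference of 4.2. Nor does any section say that volunteer examinations come before the 90% competency level in 10.5.

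What the reply does not remove is that 5.2 counts volunteers inside the patient total, so the word patients cannot be relied on to keep them out. Section 10.2 does not repeat the symptomatic restriction, and technical success and satisfaction in 10.5 carry no such limit. Tether use in volunteers is foreseeable, because 10.6 has them help with both versions. And if volunteers have no EGD, the safety gap follows directly.

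**Conclusion.** The concern holds as a conflict in the text and a gap in the analysis set, not as a demonstrated bias. Sections 5.2 and 10.6 conflict with 5.4 and 5.8 on a literal reading, and 10.2 leaves the volunteers' status to be settled after the data are in.

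The largest effect, with all 30 volunteers entering as reference-negatives, is a yield of 17.0% instead of 24.3% and an NPV of 95.2% instead of 92.5%. With 5 false positives, specificity is 93.7% instead of 89.8%. These figures rest on the assumed 21 D2 patients and 17 detections. They also take all 70 patients as analysed, although the tether condition in 10.2, read literally, would leave fewer. The effect is smaller with fewer volunteers and zero on accuracy if none has EGD. The only named comparative test is unaffected. The point merits correction because either answer on EGD leaves one of the two primary analyses with the wrong people in it.

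**What to change.** In 10.2 and 10.5, restrict the yield, accuracy, completion and satisfaction analyses to enrolled patients who meet inclusion criterion 3. Report volunteers only in the learning-curve outcome and in a separate capsule-safety listing for which EGD is not required. State the efficacy denominator as patients only: up to 70 under 10.6, to be reconciled with the synopsis figure of 100.

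Reconcile 5.2 and 10.6 with 5.4, 5.8 and 6.2 by stating the volunteers' own eligibility and procedures, including whether they undergo EGD. That choice is for the sponsor and the IRB.

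The cost is protocol wording and a smaller stated analysis number. No patient recruitment or data collection is lost.
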